6.4 STUDY INTERVENTION COMPLIANCE

Not applicable.

6.5 CONCOMITANT THERAPY

6.5.1 RESCUE MEDICINE

As inpatients, our current standard analgesic protocol will be followed: acetaminophen 975-1000 mg po QID, oxycodone 5-10 mg po q4 h prn moderate pain (NRS 4-7), and morphine 1-2 mg IV prn severe pain (NRS>7). Prior to discharge, participants will all be provided with a prescription for oxycodone (5 mg tablets) by their surgeon, as dictated by our current standard of care. If pain occurs postoperatively, participants will attempt to achieve pain relief by increasing amplitude of stimulation with the Gate Keeper app. Participants in the training run-in period with a continuous peripheral nerve block, will use their pump's integrated bolus button to administer additional local anesthetic, when needed if pain persists. If pain relief is not achieved and pain remains (NRS \geq 4), participants are instructed to take prescribed opioids q4h.

7 STUDY INTERVENTION DISCONTINUATION AND PARTICIPANT DISCONTINUATION/WITHDRAWAL

7.1 DISCONTINUATION OF STUDY INTERVENTION

Catheter/lead implantation will be discontinued if the participant requests during the procedure. The catheter/lead may be removed at any time of the participant's choosing within the first week after surgery.

7.2 PARTICIPANT DISCONTINUATION/WITHDRAWAL FROM THE STUDY

7.2.1 DISCONTINUATION CRITERIA

1. Participants may withdraw voluntarily from participation in the study at any time and for any reason.
2. Participants may be withdrawn on the basis of the Investigator's clinical judgment, protocol deviation or loss to follow-up.
3. This study may be terminated at the discretion of any regulatory agency for reasons including safety and/or efficacy.
4. The Primary Investigator may elect to discontinue or stop the study for any reason including safety.
5. When a participant withdraws or is withdrawn before completing the study, the date and reason for withdrawal are to be documented in the CRF.
6. In the event that a patient is withdrawn prematurely due to an AE or serious AE, the AE or serious AE will be followed until it resolves or stabilizes, or until it is judged by the Principal Investigator to be no longer clinically significant.

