Randomization [**all research specific**] will be stratified by anatomic location (shoulder and foot/ankle surgery) in a 1:1 ratio and in blocks of 2. Computer-generated randomization lists will be created by the UC San Diego Investigational Drug Service and the allocation provided to the investigators *via* sequential, opaque envelopes. Pulse generators are available that are capable of either (1) passing electrical current; or (2) not passing electrical current. Importantly, these 2 modes (active and sham) are indistinguishable in appearance, and therefore investigators, participants, and all clinical staff will be masked to treatment group assignment, with the only exception being the unmasked individuals who insert the RELAY and program the stimulator.

The RELAY system with the integrated needle will be inserted adjacent to the target nerve with an in-plane approach [**same as standard-of-care**]. Dextrose 5% in water (1-20 mL) will be injected via the needle to open a space around the target nerve(s) [**research specific**], the catheter advanced [**same as standard-of-care**], and the needle subsequently withdrawn [**same as standard-of-care**].

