7.3 LOST TO FOLLOW-UP

Study participants may miss data collection phone calls—it is common even though the investigators attempt multiple contacts with participants at specified times—but this study will not consider any patient "lost to follow-up". We may not be able to collect all data for all participants at all study time points; but we will continue to attempt to contact participants until 14 days have passed for that participant (the duration of study participation) or the participant requests study withdrawal (in which case it is a withdrawal and not "lost to follow-up").

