8 STUDY ASSESSMENTS AND PROCEDURES

8.1 EFFICACY ASSESSMENTS

Outcome measurements. We have selected outcome measures that have established reliability and validity, with minimal inter-rater discordance, and are recommended for pain clinical trials by the Initiative on Methods, Measurement, and Pain Assessment in Clinical Trials (IMMPACT) consensus statement. The primary outcome measure will be the median “average” daily **pain intensity** for Days 1-7 as measured with the NRS within the BPI. The primary analysis will compare the two treatments (inter-subject comparisons) in which half of the participants will receive active neuromodulation and the other half a sham/placebo neuromodulation. Endpoints will be evaluated on postoperative Days 1, 2, 3, 4, 7, 8, and 14. In addition, participants will receive a phone call the evening of postoperative Day 0 (the day of surgery) to answer any questions they may have about the stimulator or study protocol.

Each time the questionnaire is applied, participants will be instructed to respond for the previous 24 hours. The exception will be on Day 1 because at these time points, the interest is in participants’ experiences subsequent to discharge from the recovery room. During this day only, participants will be instructed to respond for the period of time since they were discharged from the recovery room.

We will record basic anthropomorphic characteristics (e.g., age, physiological sex, height, and weight), intervention characteristics (e.g., pulse generator parameters, catheter insertion duration, minimum/maximum comfortable amplitude), surgical characteristics (e.g., surgical duration) and protocol deviations / adverse events.

All data collection following the day of the intervention (Day 0) will be collected by telephone from the University of California San Diego by the investigators, Program Manager, and/or research coordinators specifically trained in these instruments’ application, minimizing inter-rater discordance and standardizing responses across all enrolling centers. Observers masked to treatment group assignment will perform all postoperative assessments. Each data collection phone call will require approximately 5 minutes.

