9.2 SAMPLE SIZE DETERMINATION

The sample size estimation is centered around the hypothesis that neuromodulation lowers the severity of pain the week after surgery. To this end, the primary outcome measure is the median "average" daily pain intensity for Days 1-7 as measured with the NRS within the BPI. This outcome measure was used by the authors previously for a similar study treating the same patient population with a different percutaneous peripheral nerve stimulation pulse generator and lead, and we therefore will use the resulting mean (SD) from each treatment group to power the present pilot study [Ilfeld et al. Anesthesiology 2021; 135: 95-110]. Specifically, the treated and sham groups reported a mean (SD) of 1.1 (1.1) and 3.1 (1.7), respectively. Assuming a standard deviation of 2.05, a sample size of 20 participants per group provides 85.2% power to detect a group difference of 2 points. With an additional 10 participants allowed to replace drop-outs in the randomized portion, a total of up to 70 participants may be enrolled in this study combining the run-in and randomized stages.

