9.4.5 BASELINE DESCRIPTIVE STATISTICS

As described above, balance on baseline covariates will be assessed using absolute standardized difference (ASD). Variables considered imbalanced will be adjusted for in the statistical analyses. Analyses will be carried out using modified intention-to-treat i.e., participants who received any study treatment will be analyzed according to the group to which they were randomized.

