10.1.9 PROTOCOL DEVIATIONS

A protocol deviation is any noncompliance with the clinical trial protocol or International Conference on Harmonisation Good Clinical Practice (ICH GCP). The noncompliance may be either on the part of the participant, the investigator, or the study site staff. As a result of deviations, corrective actions will be implemented promptly.

These practices are consistent with ICH GCP:

- Section 4.5: Compliance with Protocol, sections 4.5.1, 4.5.2, and 4.5.3
- Section 5.1: Quality Assurance and Quality Control, section 5.1.1
- Section 5.20: Noncompliance, sections 5.20.1, and 5.20.2.

It is the responsibility of the study investigator to use continuous vigilance to identify all deviations and report appropriate deviations (such as those related to an SAE) within 10 working days. All deviations must be addressed in study source documents and ultimately reported to the UCSD Office of IRB Administration.

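### Section 7.2.1 lets the investigator withdraw randomized participants from the study without securing their Day 1–7 scores, in conflict with 7.3, while 9.2 lets undefined drop-outs be replaced

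*Combined protocol and SAP*

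**What the plan says.** **Withdrawal.** Section 7.2 covers withdrawal from the study; stopping the intervention is dealt with separately in 7.1. Item 2 of 7.2.1 lets the investigator withdraw a participant for "clinical judgment, protocol deviation or loss to follow-up". After a withdrawal, 7.2.1 asks for the date and reason, and for adverse event follow-up if an adverse event was the cause. It says nothing on endpoint data.

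**Deviation.** Section 10.1.9 is broad: "A protocol deviation is any noncompliance with the clinical trial protocol", whether by participant, investigator or site staff.

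**Follow-up.** Section 7.3 says that "this study will not consider any patient" lost to follow-up. Contact attempts run until Day 14 or until the participant asks to withdraw.

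**Replacement.** Section 9.2: "With an additional 10 participants allowed to replace drop-outs in the randomized portion", up to 70 may be enrolled overall. Section 9.3 repeats the allowance of 10. Neither section defines a drop-out.

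**Safeguards.** Investigators and clinical staff are masked, "with the only exception being the unmasked individuals who insert the RELAY and program the stimulator" (6.1.1). In 8.1, "Observers masked to treatment group assignment will perform all postoperative assessments". Under 9.4.5, "participants who received any study treatment will be analyzed according to the group to which they were randomized". Section 9.4.1 expects negligible missing data and otherwise applies multiple imputation by chained equations, assuming missing at random.

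**The concern.** The primary endpoint is the median of five telephone scores, from Days 1, 2, 3, 4 and 7. If an investigator can end study participation after allocation, on grounds as wide as clinical judgment or any noncompliance, that decision may determine whether some of those scores exist. Nothing requires the person deciding to be masked, and some of the team are unmasked by design.

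Sections 7.2.1 and 7.3 also disagree. One makes loss to follow-up a ground for withdrawal; the other says the category will not be used. Section 7.3 lists two ends to contact and investigator withdrawal is neither, so staff are not told whether to keep calling someone withdrawn for a deviation.

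The replacement wording adds to this. If an investigator withdrawal counts as a drop-out, a participant with no further scores can be succeeded by a new one, and the 40 with complete data are no longer simply the first 40 randomized. With about 20 per arm, a few withdrawals related to outcome could matter. Imputation under missing at random need not correct for them, because a judgment about a patient's course can rest on information outside the dataset.

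**Working it through.** **1. The plan's own power.** Inputs from 9.2: 20 per group, difference 2, SD 2.05. Alpha is 0.05 two-sided (9.4.3). For a two-sample t-test, the noncentrality is 2 / (2.05 × √(2/20)) = 2 / 0.648 = 3.085 with 38 degrees of freedom. Power is 85.2%, matching the stated figure.

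**2. What keeping everyone does to power.** Same formula:
- 15 per group (10 of 40 without data and not replaced): 2 / (2.05 × √(2/15)) = 2.672; power 73.2%.
- 25 per group (all 50 randomized, followed and analyzed): 2 / (2.05 × √(2/25)) = 3.449; power 92.2%.

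Following and keeping withdrawn participants costs none of the planned power. The 10 extra places are 10/40 = 25% of the planned randomized sample.

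**3. Worst-case illustration.** Assumptions: no true effect; normal scores with SD 2.05; two-sided Mann-Whitney test at 0.05. The active arm draws 20 + k scores, the k highest are removed, and sham draws 20. Only completers are analyzed, so 9.4.5 and 9.4.1 are ignored. Results over repeated runs of 8,000 trials, with the rate being significance in favour of active:

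| k withdrawn | Shift in mean (NRS) | Favourable false-positive rate |
|---|---|---|
| 0 | about 0 | about 2.5% |
| 1 | about −0.2 | about 5% |
| 2 | about −0.35 | about 8% |
| 3 | about −0.47 | about 12% |

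This sketch replaces within the active arm. Section 6.1.1 would randomize any replacement 1:1. With that rule and 2 withdrawn, the favourable rate is 7.4%, so the result is close.

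**4. Milder cases.**
- Completers only, but withdrawals drawn at random from the worse half of the active arm: about 3%, 4% and 5% for k = 1, 2, 3.
- Five daily scores with an assumed within-person correlation of 0.5 to 0.7. The k worst active participants are withdrawn after Day 2 on observed pain, but kept in their arm with the median of their available days: about 2% to 2.5%, so no inflation.
- Withdrawals unrelated to outcome: no inflation.

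**5. The text side by side.** Loss to follow-up is a ground for withdrawal in 7.2.1 and is never declared in 7.3. The end of contact is Day 14 or participant request in 7.3, and is unstated for investigator withdrawal in 7.2.1. A participant withdrawn after any study treatment stays in the analysis set under 9.4.5, with later scores imputed if not collected. A participant withdrawn after allocation but before any treatment leaves the set.

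**The case against.** The best case for the plan is that the gap is narrow. Item 2 is permissive, so if 7.3 classes nobody as lost to follow-up, that ground is simply never used. Section 7.3 can be read as already requiring calls to Day 14. Modified intention-to-treat keeps treated participants in their arm, and withdrawal driven by recorded pain is compatible with missing at random. Masked staff make the assessments. This all stands, and it is why the size cannot be put higher. It does not settle whether calls continue after an investigator withdrawal, and masked assessors protect how a score is recorded, not whether it is sought.

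A reader might infer more than the documents support:
- **That withdrawal ends the calls.** No section says so; the text is silent.
- **That late-found ineligibility is the expected route.** It would count as a deviation under 10.1.9, but 7.2.1 does not name it. Records are screened beforehand (10.1.1), and 8.2 has an investigator review the criteria with the participant after consent. It is possible, not predicted.
- **That deviations show mainly in the active arm.** Sham devices are connected and programmed in the same way (6.1.1), and dislodgement or early removal can occur in either arm.
- **That unmasked inserters decide on withdrawals.** The documents do not say who decides; they only fail to exclude it.
- **That the table is a forecast.** It selects on final scores, in one arm, among completers. To select on a final score the score must already exist, and 9.4.5 would then keep it.

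**Conclusion.** The point holds as a conflict between 7.2.1 and 7.3 and as an open route to selective missing data. Decisions after allocation, not required to be masked, can determine whose Day 1–7 scores are observed and whose are imputed, and the replacement wording in 9.2 does not exclude those cases. It does not show that participants will be removed from the analysis or that the result will be biased.

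The size is unknown. About 5–12% for one to three withdrawals, against 2.5%, is an upper illustration resting on deliberate selection of the worst active outcomes and a completers-only analysis. The more plausible settings above give 2% to 5%. Because the remedy is wording and costs almost nothing, the change should be made even though the likely effect is small.

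**What to change.** - **7.2.1 item 2:** delete protocol deviation and loss to follow-up as grounds for withdrawing a randomized participant from the study, so that it agrees with 7.3.
- **7.2.1 and 7.3:** state that the scheduled calls continue to Day 14 unless the participant withdraws consent. This applies after any investigator decision (including one on clinical judgment), deviation, late-found ineligibility, early catheter removal or stopping of stimulation.
- **9.2:** state that the 10 extra participants are added to those already randomized and do not replace them, and that those already randomized stay in the analysis under 9.4.5.

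These edits concern data collection only; they leave untouched the participant's right to withdraw and all decisions on stimulation or catheter removal.

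The cost is protocol wording and a few calls of about five minutes that are already scheduled. The downside is that a few ineligible or off-protocol participants remain in the data and may slightly dilute the estimate.

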7.3 LOST TO FOLLOW-UP

Study participants may miss data collection phone calls—it is common even though the investigators attempt multiple contacts with participants at specified times—but this study will not consider any patient "lost to follow-up". We may not be able to collect all data for all participants at all study time points; but we will continue to attempt to contact participants until 14 days have passed for that participant (the duration of study participation) or the participant requests study withdrawal (in which case it is a withdrawal and not "lost to follow-up").

8 STUDY ASSESSMENTS AND PROCEDURES

8.1 EFFICACY ASSESSMENTS

Outcome measurements. We have selected outcome measures that have established reliability and validity, with minimal inter-rater discordance, and are recommended for pain clinical trials by the Initiative on Methods, Measurement, and Pain Assessment in Clinical Trials (IMMPACT) consensus statement. The primary outcome measure will be the median “average” daily **pain intensity** for Days 1-7 as measured with the NRS within the BPI. The primary analysis will compare the two treatments (inter-subject comparisons) in which half of the participants will receive active neuromodulation and the other half a sham/placebo neuromodulation. Endpoints will be evaluated on postoperative Days 1, 2, 3, 4, 7, 8, and 14. In addition, participants will receive a phone call the evening of postoperative Day 0 (the day of surgery) to answer any questions they may have about the stimulator or study protocol.

Each time the questionnaire is applied, participants will be instructed to respond for the previous 24 hours. The exception will be on Day 1 because at these time points, the interest is in participants’ experiences subsequent to discharge from the recovery room. During this day only, participants will be instructed to respond for the period of time since they were discharged from the recovery room.

We will record basic anthropomorphic characteristics (e.g., age, physiological sex, height, and weight), intervention characteristics (e.g., pulse generator parameters, catheter insertion duration, minimum/maximum comfortable amplitude), surgical characteristics (e.g., surgical duration) and protocol deviations / adverse events.

All data collection following the day of the intervention (Day 0) will be collected by telephone from the University of California San Diego by the investigators, Program Manager, and/or research coordinators specifically trained in these instruments’ application, minimizing inter-rater discordance and standardizing responses across all enrolling centers. Observers masked to treatment group assignment will perform all postoperative assessments. Each data collection phone call will require approximately 5 minutes.

In addition to the outcomes described below, we will record awakenings due to pain at each data collection phone call, as well as any sensory deficits for participants with continuous peripheral nerve blocks, and patient-controlled changes to the neuromodulation amplitude. On postoperative day 1 we will query participants on whether they believe they are receiving active or sham stimulation (a masking assessment).

Hypothesis 1: Neuromodulation with the RELAY device will decrease **pain intensity** for Days 1-7 following foot and shoulder surgery currently treated with a single-injection peripheral nerve block (as measured with the NRS within the BPI).

Current/present, worst, least, and average ‘surgical pain will be assessed using the NRS as part of the BPI (short form), with the “average” pain scores collected on postoperative days 1, 2, 3, 4 and 7 designated as the primary endpoint. The NRS is a highly-sensitive measure of pain intensity with numbers ranging from 0 to 10, zero equivalent to no pain and 10 equivalent to the worst imaginable pain. The NRS has been demonstrated to be a valid and reliable measure in multiple pain states and following analgesic interventions. In addition, NRS scores correlate well with other measures of pain intensity, and demonstrate high test-retest reliability in chronic nociceptive and neuropathic pain states. These NRS characteristics led to recent IMMPACT consensus recommendations for use of the 10-point NRS of pain intensity for pain trials.

Hypothesis 2: Neuromodulation with the RELAY device will decrease **opioid consumption** within the week following foot and shoulder surgery currently treated with a single-injection peripheral nerve block (measured in oxycodone equivalents), as measured both with daily and cumulative opioid consumption within the first postoperative week).

Opioid analgesic consumption will be recorded at all time points (Table 2), with the secondary outcome measure of greatest importance being the cumulative opioid dose in oral oxycodone equivalents for the first 7 postoperative days following recovery room discharge. The two treatment groups' daily opioid consumption will also be compared at all timepoints, including Day 14.

Hypothesis 3: Physical and emotional functioning as measured with the Interference Subscale of the BPI. Neuromodulation with the RELAY device will decrease pain's **interference** in physical and emotional **functioning** within the week following foot and shoulder surgery currently treated with a single-injection peripheral nerve block.

It is well-recognized that, "pain is a complex, multidimensional, sensory, and emotional experience that is individually perceived and described in many different ways." This observation has led to consensus recommendations that "multiple core domains and related measures be considered in pain treatment trials," that "tap into a wider experience of pain over time and its impact on functioning and quality of life." Therefore, the proposed trial will include the BPI, an instrument that includes—in addition to pain intensity scales—seven measures evaluating the pain's interference with physical and emotional functioning, such as sleep, relations with others, and enjoyment of life. It is this 7-question Interference Scale that will be used specifically for Hypothesis 3. The BPI has been used and validated in countless clinical pain-related studies. This instrument is associated with minimal subject burden and is easily interpreted by participants of all ages and education levels. It has high test-retest reliability and correlates well with much longer questionnaires, including the McGill measures and EuroQol. The secondary outcome measures of greatest interest after the cumulative opioid consumption will be the Interference Scale (0-70) recorded on Day 3.

